Subjects with a **normal level** of serum Vitamin D 30-100 ng/ml at time of enrollment will be automatically enrolled in the controlled group and will be followed only for long-term progression free survival and outcome. No further evaluation of serum 25-hydroxyvitamin D [25(OH) D] will be obtained.

Subjects found to have **low levels** of serum Vitamin D <30 ng/ml at time of enrollment will be randomized on a 1:1 basis to receive vitamin D 5000 IU daily (Higher Dose Cohort) or vitamin D 1000 IU daily (Lower Dose Cohort) stratified by disease group (aggressive NHL or indolent NHL/CLL).

Evaluation: Serum 25-hydroxyvitamin D levels will be assessed at baseline, 6 months from baseline, 12 months from baseline, and then year 2 and 3. If subject is at a normal level of 25-hydroxyvitamin D [25(OH) D], no change in intervention will be made. If the subject has a low level of vitamin D, which is defined as < 30 ng/ml, then the dose that they are currently enrolled in will be increased by 1000 IU (e.g. 5000 IU increase to 6000 IU; 1000 IU increase to 2000 IU). There will be a maximum dose of 10000 IU daily. If a subject has an elevated level of vitamin D, which is defined as > 100 ng/ml, then the dose will be held for one month and the level will be rechecked. If the level returns < 100 mg/ml, the dose will be cut in half and re-tested in two months. PFS and OS will be assessed at the end of study (3 years).

Schema:

**A Pilot Study of Vitamin D Replacement in Patients with
Non-Hodgkin's Lymphoma and Chronic Lymphocytic Leukemia
With Low Vitamin D Levels**

[figure not shown]

Table of Contents

Abstract	Page 2
Schema	Page 3
Section 1.0 Objectives	Page 5
Section 2.0 Background	Page 5
Section 3.0 Eligibility Criteria	Page 11
Section 4.0 Registration/Randomization Procedures	Page 11
Section 5.0 Treatment Plan	Page 13
Section 6.0 Measurement of Effect	Page 15
Section 7.0 Study Parameters	Page 17
Section 8.0 Drug Formulation and Procurement	Page 18
Section 9.0 Toxicity Reporting Guidelines	Page 28
Section 10.0 Statistical Considerations	Page 31
Section 11.0 Records to Be Kept	Page 34
Section 12.0 Patient Consent Form Statement	Page 34
Section 13.0 References	Page 36
Section 14.0 Data Forms	Page 38
Appendix A Eligibility checklist	Page 39
Appendix B NCI Common Toxicity Criteria Version 4.0 (CTCAE)	Page 41
Appendix C FDA MEDWATCH form	Page 41
Appendix D Oral, Sublingual, and/or Buccal Route Medication Adherence Standard Procedure (V 1.0 11-25-2013)	Page 42

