Control group subjects: disease status must be assessed at the end of 3 years. Three years is defined as from the time of registration confirmation to day 1095 (+/- 180 days). For subjects no longer being followed by the study site, an attempt should be made by contacting the referring physician or reaching out to the subject at the 3-year time point to assess survival or progression free survival status. Contact and subject status should be documented in the medical record.

Covid Visit Exceptions:

If a subject visit is cancelled due to Covid concerns, then the study staff will confirm with the subject that they have an adequate supply of the study vitamin D supplement to continue daily dosing as prescribed.

The lab work required for the study will be collected at their next visit.

The Vitamin D administration diary may be collected at their next visit or via US Mail.

The visit will be documented as delayed due to Covid. The visit schedule will otherwise be maintained so that subject is on study for 3 years per protocol. The above will be fully documented in the medical record.

Dose Modifications based on vitamin D levels at 6 month, 12 month and year 2 and 3.

If subject is at a **normal level** (30-100 ng/ml) of 25-hydroxyvitamin D [25(OH) D], no change in intervention will be made.

If the subject has a **low level** of 25-hydroxyvitamin D [25(OH) D], which is defined as [OH] D < 30 ng/ml, then the dose that they are currently enrolled in will be increased 1000 IU (e.g. 5000

IU increase to 6000 IU; 1000 IU increase to 2000 IU). There will be a maximum dose of 10000 IU daily.

If a subject has an **elevated level** of 25-hydroxyvitamin D [25(OH) D], which is defined as [OH] D > 100 ng/ml, then the dose will be held for one month and a level will be rechecked. If the repeat level is < 100 mg/ml, the dose will be cut in half and re-tested in two months.

After the 12 month time point, if Vitamin D levels are not within normal limits, the investigator may manage subjects as clinically indicated, i.e. levels can be monitored more frequently than annually. Dose adjustment will be managed according to guidelines above or as recommended by the patient's primary care physician or Endocrinologist.

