6.2 Survival

Subjects will be analyzed with respect to overall and progression-free survival.

Overall survival is defined as time from study entry until death from any cause. For subjects who are still alive at the time of the study analysis or are lost to follow-up, survival will be censored at the last recorded date that the subject was known to be alive.

Progression-free survival is defined as time from study entry until the first notation of clinical progression, relapse, starting new therapies or death from any cause. For subjects who are still progression-free at the time of the study analysis or are lost to follow-up, progression-free will be censored at the last recorded date that the subject was known to be progression-free.

Response will be determined by the Principal Investigator or the lead site investigators.

Section 7.0 Study Parameters:

	Low Levels <30 ng/mL - RANDOMIZED GROUP					
	Pre-Treatment (within 30 days of Consent)	First Dose	6 months Day 182 (+/- 30 Days)	12 months Day 365 (+/- 30 Days)	Year 2 Day 730 (+/- 30 Days)	Year 3 Day 1095 (+/- 30 Days) End of Study
History & Physical	X					
Height, Weight, Vital Signs	X					
Monitor for Vitamin D related AEs			X	X	X	X
Serum Calcium	X					
Serum 25- hydroxyvitamin D [25(OH) D]	X		X	X	X	X
Vitamin D		X - Daily Dosing at Home for 3 years				
Long-term progression free survival and outcome ¹						X

Normal Level $\geq 30\text{ng/ml}$ - CONTROL GROUP*		
Followed only for long-term progression free survival and outcome. No further evaluation of serum 25-hydroxyvitamin D [25(OH) D] will be obtained. (NOTE: subjects currently taking Vitamin D supplements will be encouraged to continue their supplementation.)		
Required studies	Pre-Treatment (Within 30 days of Consent)	Year 3 - Day 1095 (+/- 180 Days) End of Study
History & Physical	X	
Height, Weight, Vital Signs	X	
Serum Calcium	X	
Serum 25-hydroxyvitamin D [25(OH) D]	X	
Long-term progression free survival and outcome ¹		X

¹ Progression defined as relapse, progression, or starting new therapies, or death

Section 8.0 Drug Formulation and Procurement (per UNMC Lexicomp Online):

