10.1 Patient Accrual

Subjects found to have low levels of serum Vitamin D <30 ng/ml at time of enrollment will be randomized on a 1:1 basis to receive vitamin D 5000 IU daily (Higher Dose Cohort) or vitamin D 1000 IU daily (Lower Dose Cohort) stratified by disease group aggressive NHL (fast-growing tumors) or indolent NHL/CLL (slow-growing tumors).

The sample size calculations are based on the primary endpoint of 3-year PFS. The expected PFS for patients with low levels of serum Vitamin D is 45%.⁴⁴ The 3 year PFS of the low dose and high dose groups will each be compared to a historical fixed expected 3-year PFS of 45%.⁴⁴ The sample size calculations are based on a single arm survival calculation based on an assumption of exponentially distributed PFS times using a 3-year PFS of 60% for each of the randomized arms (low dose or high dose). Therefore, the sample size calculations are based on detecting a 15% difference in 3-year PFS for each randomized arm (low dose or high dose) vs.

a historical fixed expected PFS of 45%. Since such single arm studies are typically conducted as a one-sided test, we use $\alpha = 0.025$, however, no other adjustments will be made for multiplicity. Sample size calculations were conducted using the SWOG statistical calculator found at https://www.swogstat.org/stat/public/one_survival.htm.

Using a one sided test with accrual time of 2 years, follow-up time of 3 years, $\alpha = 0.025$, a null PFS of 45% and an alternative PFS of 60% a total of 230 eligible patients will be enrolled in the normal serum Vitamin D group based on current accrual rate and until 70 eligible patients in each randomized arm (low or high dose) to provide 80% power. These results assume that two sequential tests are made (1 interim analysis and the final analysis) using the O'Brien-Fleming spending function to determine the test boundaries. Our final enrollment is projected to be 370 patients expecting a ~10% loss to follow-up/inevaluability rate.

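### Section 10.1 claims 80% power from 3 to 5 years of follow-up per patient, but the schedule plans no PFS assessment after Day 1095; with 3-year follow-up each arm has about 70%

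*Combined protocol and SAP*

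**What the plan says.** **The calculation.** Section 10.1 assumes a single-arm survival test with an "assumption of exponentially distributed PFS times using a 3-year PFS of 60% for each of the randomized arms", compared with a fixed 45%, at one-sided alpha 0.025. The time inputs are given as "Using a one sided test with accrual time of 2 years, follow-up time of 3 years", and randomised enrolment runs "until 70 eligible patients in each randomized arm (low or high dose) to provide 80% power". Section 10.2.3 names the test: a one-sample logrank test for each arm.

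**The data collection.** In the Section 7.0 table for the randomised group, the last column is "Year 3 Day 1095 (+/- 30 Days) End of Study", and the PFS/outcome row is marked in that column only. The Abstract places the PFS and OS assessment at the end of study and gives that as 3 years. The Covid exceptions in Section 5.2 add: "The visit schedule will otherwise be maintained so that subject is on study for 3 years per protocol". The OS censoring text in Sections 1.2 and 10.0 refers to a study analysis at 3 years. No visit, contact or status check of randomised patients after Day 1095 is planned.

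**The censoring rule.** Section 6.2 censors patients who are progression-free when the study is analysed at the last date they were known to be so. It sets no Day-1095 limit and no common closing date.

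**The concern.** In a survival sample-size calculation, 2 years of accrual followed by 3 years of follow-up means that the first patient is observed for 5 years and the last for 3. The conduct sections describe 3 years for each patient. The power of a one-sample logrank test depends on the number of events, so events expected in years 3 to 5 but never sought are lost power. This is the primary endpoint. If the assumed follow-up is not collected, the chance of missing the sponsor's own target effect in an arm is larger than the 20% that the plan implies, and a non-significant arm would be weaker evidence against benefit than readers would take it to be.

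**Working it through.** **Inputs (Section 10.1).** n = 70 per arm; one-sided alpha 0.025 (z = 1.960); 3-year PFS 45% under the null and 60% under the alternative; exponential times; accrual 2 years, then 3 years of follow-up.

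**Hazards per year.** Null: L0 = -ln(0.45)/3 = 0.2662. Alternative: L1 = -ln(0.60)/3 = 0.1703. Ratio L1/L0 = 0.640.

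**Step 1: reproduce the plan's 80% (3 to 5 years per patient, uniform accrual).**
- Event probability under the alternative: 1 - (e^(-3 L1) - e^(-5 L1))/(2 L1) = 1 - (0.600 - 0.427)/0.3406 = 0.491. Observed events D = 70 x 0.491 = 34.4.
- Events expected from the null hazard over the same person-time: E = D/0.640 = 53.8.
- One-sample logrank formula: power = Phi{[(E - D)/sqrt(E) - z] x sqrt(E/D)} = Phi{[2.642 - 1.960] x 1.250} = Phi(0.853) = 80.3%. The n for 80% is 70.
- Cube-root exponential formula: power = Phi{[1 - r - z/(3 sqrt(d0))] / [r/(3 sqrt(d1))]}, with r = 0.640^(1/3) = 0.862, d0 = 45.6 events under the null and d1 = 34.4 under the alternative. This gives 80.2%, and again n = 70.

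Both formulas return the stated sample size, which supports the 3-to-5-year reading.

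**Step 2: end follow-up at 3 years for every patient.**
- D = 70 x (1 - 0.60) = 28.0; E = 28.0/0.640 = 43.8.
- Logrank formula: Phi{[2.384 - 1.960] x 1.250} = Phi(0.530) = 70.2%.
- Cube-root formula, with d0 = 70 x 0.55 = 38.5 and d1 = 28.0: 72.9%.

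**Step 3: simulate the planned test**, (O - E)/sqrt(E), in at least 200,000 trials per setting. Simulated one-sided type I error is about 0.020 in both settings, so the test is somewhat conservative. That is why the simulated values lie below the formula values.

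| Method | 3 to 5 years | 3 years | Drop (points) |
|---|---|---|---|
| Expected events per arm | 34.4 | 28.0 | |
| One-sample logrank formula | 80.3% | 70.2% | 10 |
| Cube-root formula | 80.2% | 72.9% | 7 |
| Simulation | 77.9% | 68.9% | 9 |

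**Sensitivity.** At the final-analysis level of 0.024501 (Section 10.4.1), the logrank formula gives 80.0% and 69.8%. If every patient is seen at the end of the +30-day window, simulated power is 70.0%. For scale, 80% power with 3-year follow-up would need 84 (cube-root), 86 (logrank formula) or about 90 (simulation) patients per arm.

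**The case against.** **The cap is inferred.** A reader might infer that the protocol discards every event after Day 1095. The documents do not say that. The Section 6.2 rule runs to the time of the study analysis and is compatible with a common cut-off, and two of the supporting statements are soft: one sits in the Covid exceptions, and the Abstract's end of study can be read per patient or per study. This stands, and it makes the result conditional. It does not remove the mismatch, because any events after 3 years would come from unplanned charting that may differ by site, while 10.1 counts on them.

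**The calculator's formula is not shown.** Other variants give about 71% to 85% at n = 70 with the stated inputs. One of them, on the mean-survival scale, gives 79.9% with 3-year follow-up. A reader might use it to argue that the 80% already describes 3-year follow-up. But it gives 84.7% for the 2-year accrual and 3-year follow-up that 10.1 states, so it does not reproduce the plan. Every variant examined loses about 5 to 10 points.

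**Mixed methods.** Setting the stated 80% against the simulated 69% would suggest an 11-point loss. About 2 of those points are the difference between formula and simulation. Nor do the figures show that 70 is miscalculated on its own inputs: two formulas return exactly 70.

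**It is a pilot.** True, and the mismatch neither inflates type I error nor biases the Kaplan-Meier estimates. The plan nevertheless states a formal power, a formal test and an interim boundary, so the power statement should fit the data to be collected.

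**Conclusion.** The point holds in conditional form: the 80% in Section 10.1 rests on follow-up that the schedule does not plan and that the censoring rule does not secure. If follow-up ends at 3 years as scheduled, expected events per arm fall from about 34 to 28. Power falls to about 70% (69% to 73% across the simulation and the two formulas that reproduce the plan), a like-for-like loss of 7 to 10 points. The chance of missing the target effect in an arm rises from the stated 20% to about 27% to 31%.

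This assumes exponential PFS, uniform accrual over 2 years, 70 patients per arm and no loss to follow-up. The roughly 10% loss mentioned in 10.1 is a separate matter and is not in these figures. The documents do not support the stronger claim that later events are excluded; if sites did record PFS beyond Day 1095, power would lie between the two sets of figures.

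**What to change.** **Option 1: correct the statement.** In 10.1, give power as about 70% per arm for 3-year follow-up with 70 patients, and name the formula. In 6.2, state that PFS is censored at 3 years. The cost is a few words and a less favourable figure.

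**Option 2: collect what was assumed.** In 6.2 and 7.0, state that PFS and OS status of every randomised patient is recorded up to one common data cut-off, when the last randomised patient reaches Day 1095. Power returns to about 78% to 80% if accrual takes 2 years as assumed. No extra patients are needed, and the practical cost is one further status check for earlier enrollees.

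Option 2 also has a statistical cost. The only reference value is 45% at 3 years. Counting events in years 3 to 5 carries the exponential null beyond it, to an implied 5-year PFS of 0.45^(5/3) = 26% that the documents do not support, in a population mixing aggressive and indolent disease. If Option 2 is chosen, 10.2.3 should state this assumption.

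### The planned enrolment of 370 contains no allowance for the roughly 10% loss the plan expects, so the stated 80% power is a no-loss figure; with that loss it is about 75–78%

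*Combined protocol and SAP*

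**What the plan says.** Section 10.1 (Patient Accrual) sizes each randomised arm separately against a fixed historical 3-year PFS. The method is a "single arm survival calculation based on an assumption of exponentially distributed PFS times", with "a null PFS of 45% and an alternative PFS of 60%", one-sided alpha 0.025, and these timings: "Using a one sided test with accrual time of 2 years, follow-up time of 3 years".

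Three enrolment figures follow in the same paragraph:

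- Normal-level group: "a total of 230 eligible patients will be enrolled in the normal serum Vitamin D group".
- Randomised arms: "until 70 eligible patients in each randomized arm (low or high dose) to provide 80% power".
- Total: "Our final enrollment is projected to be 370 patients expecting a ~10% loss to follow-up/inevaluability rate".

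Other sections fix how losses are treated. Sections 10.2.1 and 10.2.2 put every randomised patient into the efficacy analyses. Section 6.2 censors a patient lost to follow-up at the last date known to be progression-free. Section 10.2.3 names the one-sample log-rank test for each randomised arm. Section 10.3 defines an evaluable patient, but neither 10.2.2 nor 10.2.3 uses that definition for the primary test.

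**The concern.** A sample-size paragraph that names a loss rate beside its final total leads the reader to think the total covers that loss. Here it cannot, because the total equals the sum of the three group requirements. Either the 370 is short of what the paragraph implies, or the 80% does not apply under the loss that the same paragraph expects. The power statement is the only justification given for the size of the randomised part. A non-significant arm at the end of the trial would be interpreted against it.

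**Working it through.** **Inputs (Section 10.1 unless noted).** Null 3-year PFS 45%, alternative 60%, exponential; one-sided alpha 0.025 (z = 1.960); 80% power (z = 0.842); accrual 2 years, then 3 years of follow-up, so uniform accrual gives each patient 3 to 5 years; 70 per arm; 230 normal-level; total 370; loss about 10%. Test: one-sample log-rank (Section 10.2.3).

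**Step 1: the total.** 230 + 70 + 70 = 370. The margin for loss is zero.

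**Step 2: is 70 already inflated?** Hazards are λ0 = −ln(0.45)/3 = 0.2662 and λ1 = −ln(0.60)/3 = 0.1703 per year, a hazard ratio of 0.640. With 3 to 5 years of follow-up the event probability is p = 1 − (e^(−3λ) − e^(−5λ))/(2λ), which is p0 = 0.651 under the null and p1 = 0.491 under the alternative.

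- One-sample log-rank: the expected count per patient under the alternative is e1 = p1/HR = 0.768. Then n = [(1.960·√e1 + 0.842·√p1)/(e1 − p1)]² = [(1.718 + 0.590)/0.2768]² = 69.5, so 70.
- Cube-root-hazard test, with f = λ^(1/3): n = [(1.960·f0/(3√p0) + 0.842·f1/(3√p1))/(f0 − f1)]² = [(0.5208 + 0.2218)/(0.6433 − 0.5543)]² = 69.6, so 70.

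The plan's figure is reproduced with no dropout term. The alternative explanation is that 70 is an inflated 63 (63/0.9 = 70). None of the other variance choices tried at one-sided 0.025 gives 63; they range from 66 to 86. A 63 appears only from a log-hazard formula at one-sided 0.05, which is not the plan's alpha. So 70 is the no-loss requirement.

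**Step 3: expected full follow-up.** 70 × 0.9 = 63 per randomised arm; 370 × 0.9 = 333 overall.

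**Step 4: power under the expected loss.** The log-rank formula is power = Φ{[(e1 − p1)√n − 1.960·√e1]/√p1}.

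- n = 70, no loss: Φ{(2.316 − 1.718)/0.701} = 80.3% (cube-root 80.2%; simulation about 78%).
- n = 70, with 10% lost gradually by year 3 and censored. The assumed constant loss hazard is −ln(0.9)/3 = 0.0351 per year. Then p1 = 0.462 and e1 = 0.722, and power is Φ{(2.176 − 1.665)/0.680} = 77.4% (cube-root 77.9%; simulation about 75%).
- n = 63, as if seven patients per arm contributed nothing: Φ{(2.197 − 1.718)/0.701} = 75.3% (cube-root 75.9%; simulation about 73%).

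The simulations apply the log-rank statistic to exponential data and run about two points below the formulas even with no loss. Each figure should therefore be compared with the baseline from the same method.

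**Step 5: conventional inflation, for reference.** 70/(1 − 0.10) = 77.8, so 78 per randomised arm, and 230 + 2 × 78 = 386 in total.

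**The case against.** Four points can be made for the plan, and each one limits the finding.

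- **Nobody leaves the primary test.** A reader might infer that only 63 per arm will be analysed. The documents do not support that. Sections 10.2.1, 10.2.2 and 6.2 keep all 70 in the test and censor the losses, and the evaluability definition in Section 10.3 removes no one from it. What is lost is follow-up time. This stands, and it makes the gradual-loss figures the applicable ones; the n = 63 figures are a lower bound.
- **The sentence may only disclose the loss.** It does not say that 370 was inflated. It can be read as reporting that about 10% of the 370 will be lost. That reading is fair, but then the 80% quoted in the preceding lines needed restating for that loss, and it was not.
- **Much lower power figures belong elsewhere.** If follow-up stops at Day 1095 for every patient (the Section 7.0 schedule), simulated power is about 69% with no loss and 67% with gradual loss. It would be tempting to set 67% against the stated 80% and blame the missing allowance. The allowance explains only about 2 of those points. The rest comes from the cap and from the gap between formula and simulation, both present with no loss at all.
- **The control group needs no inflation.** Inflating all three groups would give 256 + 156 = 412. But the 230 normal-level patients have no powered comparison: Section 10.1 sets their number by accrual rate, and Section 10.2.3 only displays their curve. The documents give no basis for 412.

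**Conclusion.** The point holds in a limited form. The 370 is the plain sum of the group sizes, the 70 per arm is the no-dropout number, and no other section adds a margin. Under the plan's own 10% expectation the 80% power is overstated by about 2 to 3 points if losses are gradual and censored, and by about 5 points in the extreme case where seven patients per arm contribute nothing. These figures rest on exponential PFS, uniform accrual over 2 years with 3 to 5 years of follow-up, a constant loss hazard that reaches 10% at year 3, and loss unrelated to prognosis. They depend on the 10% actually occurring.

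No test, boundary, population or endpoint changes. For a study that calls itself a pilot, this should be fixed, but it does not undermine the design.

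**What to change.** Revise the end of the sample-size paragraph in Section 10.1 to say three things:

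1. 370 is the number enrolled (230 + 70 + 70), with no inflation for loss.
2. With about 10% loss, about 63 patients per randomised arm are expected to be fully followed, while all 70 remain in the intention-to-treat analysis with losses censored.
3. Power under that loss is about 75–78%, in place of 80%, with the calculation method and the follow-up assumption (3 to 5 years per patient) named beside it.

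The cost is one or two sentences and a slightly less favourable power figure. No patients are added and no analysis changes.

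Enrolling more is an option, not a requirement. If the sponsor preferred to keep 80%, the conventional figure is 78 per randomised arm, 386 in total. Because censored patients still contribute, about 75 per arm already restores the simulated no-loss power under the gradual-loss assumption.
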